10.4 Vital Signs and Physical Examination

Individual subject listings of measured values for physical examinations, vital signs, and body weight data will be presented. The vital signs (blood pressure, heart rate, respiratory rate and body temperature) and body height, weight data will be presented in Listing 16.2.9, and physical examination will be presented in Listing 16.2.10, and the summary results of vital signs for baseline, end of treatment, end of study, and change from baseline to end of treatment and end of study will be presented as Table 14.3.4. In addition, the summary results of physical examination will be presented as Table 14.3.5.1, and the physical examination transition status will be presented as Table 14.3.5.2.

10.5 Other Variables Related to Safety

ECOG

The observed values of ECOG performance status will be listed in Listing 16.2.11.

Electrocardiograms (ECGs)

Electrocardiogram will be listed by subject in Listing 16.2.12. The observed values are included heart rate, RR interval, PR interval, QRS duration, QT interval and overall ECG result. In addition, the summary results of electrocardiogram will be presented as Table 14.3.6.1, and the overall ECG result transition status will be presented as Table 14.3.6.2.

Statistical Analysis Plan

Telephone Contact

The telephone contact included survival status and AEs check will be listed in Listing 16.2.13.

Unscheduled visit

The unscheduled visit data will be listed in Listing 16.2.14.

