- (3) Any OTC medication other than those listed in the Concomitant Treatment section.
- (4) Dietary supplements, herbal supplements or herbal tea.
- (5) Insulin
- (6) Anti-androgens
- (7) 5-alpha reductase inhibitors
- (8) Systemic corticosteroids > 10 mg/d

X. Statistics:

1. Primary hypothesis: superiority non-inferiority equivalence other
2. Sample size: This is a Safety Extension study to Protocol FP01C-13-001. No efficacy analysis will be conducted under this protocol. No sample size calculations have been conducted for this study.
3. Efficacy population: ITT PP other: NONE
(1) No efficacy analysis will be conducted in this study.
Safety population: ITT PP other:
(1) The Safety population will consist of any subject receiving a dose of LMIS 50 mg under Protocol FP01C-13-001-EX.
4. Statistical method(s) for efficacy/ safety evaluations:
 - (1) No statistical analysis of efficacy will be conducted for this Safety Extension study
 - (2) Adverse events will be coded with MedDRA and a summary frequency table of adverse events will be provided. The severity and relationship to study medication of adverse events will be summarized as well. Furthermore, if any serious adverse events occur, the brief summary about serious adverse events will be described and listed in tables.
 - (3) The change of laboratory data, vital signs and 12-lead resting electrocardiograms (ECGs) will be summarized and assessed by paired t-test or Wilcoxon signed-rank test at a significance level of 0.05.

XI. Schedule of Assessments

	Scrn ¹ (Subjects from FP01C-13-001 who completed study more than 28 days ago)	Scrn ² (Subjects who completed the study within the last 28 days)	Treatment				ET ¹ /EOS
Visit	1	1	2	3	4	5	6
Day (from completion of 12 months of treatment with LMIS 50 mg under FP01C-13-001)	-28-0	-28-0	0	84	168 ³	252	336
Informed consent	X	X					
Inclusion/Exclusion criteria	X	X					
Demographics	X	X					
Vital signs and height (as measured in Protocol FP01C-13-001) and weight ⁶ (resting 3 minutes)	X	X	X	X	X	X	X
ECOG PS	X	X					
Physical Exam	X			X	X	X	X
12-Lead ECG (Supine 5 minutes)	X				X		X
Laboratory							
Hematology ⁶	X			X	X	X	X
Biochemistry ⁷ (Fasting)	X			X	X	X	X
Urinalysis ⁸	X			X	X	X	X
HgbA1c (Fasting)	X						X
PSA	X			X	X	X	X
Testosterone	X				X ⁹		
Study treatment			X		X		
Concomitant treatments			X	X	X	X	X
Adverse events	X	X	X	X	X	X	X

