5.5. Warning and Precautions

Leuprolide acetate has the following established significant adverse events:

- Clinical testosterone flare reaction in men with prostate cancer

- Osteoporosis

Like other LH-RH analogs, leuprolide acetate causes a transient increase in the serum concentration of testosterone during the first week of treatment. This effect may cause subjects to experience a worsening of symptoms or an onset of new symptoms including bone pain, neuropathy, hematuria, or ureteral or bladder outlet obstruction. Long-term use of an LHRH agonist has been reported to decrease bone mineral density which can increase the risk of osteoporosis and skeletal bone fractures.

Other reported adverse events of leuprolide acetate include hypogonadism, reduction in glucose tolerance, anemia, and prolongation of the QT/QTc interval.

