7.2.2. Hematological / Biochemistry Examinations

Fasting blood samples will be collected for hematological, biochemistry and biological examinations.

Hematological tests will include complete blood count (CBC), including hemoglobin (Hb), hematocrit (Hct), red blood cells (RBC), white blood cells (WBC), WBC differential (neutrophils, eosinophils, basophils, lymphocytes and monocytes) platelet counts and HgbA1c. Biochemistry tests will include ALT, AST, ALP, total bilirubin, BUN, Serum Cr, electrolytes (K, Na, Mg, Ca and P), blood glucose and lipid profile (LDL, HDL, triglycerides).

Laboratory tests, except for the HgbA1c, will be performed during the Screening Visit and at Day 84 ±7 days, Day 168±7 days, Day 252 ±7 days and Day 336±7 days. The HgbA1c will be performed at the final visit (Day 336 or End of Study Visit).

PSA will be performed at Day 84±7 days, Day 168±7 days (prior to dosing), Day 252±7 days, and at the final visit (Day 336±7 days or End of Study Visit).

The End of Study laboratory tests, HgbA1c and PSA assessments for Protocol FP01C-13-001 will be used as the Baseline assessment for this study.

Blood samples for laboratory tests will be collected in the hospital or at the investigative site and will be sent to the Central Laboratory for analyses.

*If the patient completed 12 months of treatment with LMIS 50 mg more than 28 days prior to entering the Extension study, the testosterone level should be repeated and the repeat test should indicate that the patient maintains a castrate-level of testosterone. In addition, the ECOG, PE, ECG, laboratory and PSA tests should be repeated.

If the patient has completed 12 months of treatment with LMIS 50 mg under Protocol FP01C-13-001 within the last 28 days, they will be allowed to enter the Extension study without repeating the testosterone measurements, ECG, PE, laboratory and the PSA tests.

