7.2.4. ECG

An ECG will be performed by standard 12-lead at the Screening Visit for eligibility and on Day 168±7 days prior to dosing and on Day 336±7 days (or End of Study Visit).

*If the patient completed 12 months of treatment with LMIS 50 mg more than 28 days prior to entering the Extension study, the testosterone level should be repeated and the repeat test should indicate that the patient maintains a castrate-level of testosterone. In addition, the ECOG, PE, ECG, laboratory and PSA tests should be repeated.

If the patient has completed 12 months of treatment with LMIS 50 mg under Protocol FP01C-13-001 within the last 28 days, they will be allowed to enter the Extension study without repeating the testosterone measurements, ECG, PE, laboratory and the PSA tests.

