10.3. Safety analysis

The transition matrix will be summarized for the following:

- Change from baseline in vital signs (BP, HR, RR)
- Change from baseline in physical examinations (including weight)

The summary results of vital signs (BP, HR, RR) and weight at Baseline, End of Study Visit, and the change from baseline will be summarized descriptively. Also the change from baseline to the End of Study Visit will be tested by paired t-test or Wilcoxon

signed-rank test at a significance level of 0.05.

The transition matrix of physical examination will be summarized.

- Change in laboratory data, including liver function (AST, ALT, ALP), renal function (BUN, Serum Cr), complete blood count with platelets, clinical chemistries (K, Na, Mg, Ca and P), urinalysis, serum glucose, and lipid profile (LDL, HDL, triglycerides) and HgbA1c

The summary results of laboratory data at the Baseline and the End of Study Visit, and change from baseline to End of Study Visit will be summarized by descriptive statistics and paired t-test or Wilcoxon signed- rank test will be used at a significance level of 0.05.

- Adverse event (AE) reporting

The analysis of adverse events will be tabulated by system organ class (SOC) and preferred terms according to the current MedDRA dictionary. Preferred terms will be used and presented as standardized tabulations by frequency and incidence rates. Adverse event incidence rates will be analyzed by severity and relationship to study drug. Any adverse event leading to death, discontinuation from the study, or change of dose will be listed as per regulation.

If any serious adverse event occurs, a brief summary about the serious adverse event will be described and listed.

- Change in 12-lead resting electrocardiograms (ECGs)

The summary results of 12-lead resting ECG at Baseline and the End of Study Visit will be summarized descriptively. The transition matrix for ECGs will be summarized.

11. Study Administrative Structure

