3.5 Endpoints

Determine the safety and tolerability by:

- 1) Assessment of clinically significant abnormal lab data, including liver function (AST, ALT, ALP), renal function (BUN, Serum Cr), complete blood count with platelets, clinical chemistries (K, Na, Mg, Ca and P), urinalysis, serum glucose, lipid profile (LDL, HDL, triglycerides) and HgbA1c
- 2) Adverse event (AE) reporting
- 3) Clinically significant changes from baseline in 12-lead resting electrocardiograms (ECGs) per the Investigator's judgment

The safety endpoints include:

- Adverse event (AE)
- Laboratory data
- Vital signs
- Physical examination
- 12-lead resting electrocardiograms (ECGs)

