4.1 Continuous endpoints

Descriptive statistics including number of observation, mean, median, standard deviation, standard error, minimum and maximum will be presented for the raw data. Paired T-test or Wilcoxon Signed Rank test will be used to assess the change from baseline.

Statistical Analysis Plan

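### The ECG outputs summarise and test only uncorrected QT, although RR comes from the same tracings; no planned output gives the within-subject change in heart-rate-corrected QT.

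*SAP*

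**What the plan says.** SAP 10.5 fixes the recorded ECG quantities: "The observed values are included heart rate, RR interval, PR interval, QRS duration, QT interval and overall ECG result". Listing 16.2.12 prints them by subject and visit, with no corrected QT and no change column. Table 14.3.6.1 summarises raw QT at Screening, Day 168 and Day 336, with change rows at the two later visits. In the table shell the Day 336 QT change has a P-value row and the Day 168 change has none. The test comes from SAP 4.1: "Paired T-test or Wilcoxon Signed Rank test will be used to assess the change from baseline". HR and RR have their own rows in the same table, and Table 14.3.6.2 is a transition table of the overall interpretation.

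The ECG endpoint in SAP 3.5 is a matter of judgment: "Clinically significant changes from baseline in 12-lead resting electrocardiograms (ECGs) per the Investigator's judgment".

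Corrected QT is mentioned once in the two documents, in Protocol 5.5: "Other reported adverse events of leuprolide acetate include hypogonadism, reduction in glucose tolerance, anemia, and prolongation of the QT/QTc interval". No correction formula appears anywhere.

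Two related passages bear on any ECG change analysis.

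- **Testing.** Synopsis X.4(3) calls for a test, stating that "12-lead resting electrocardiograms (ECGs) will be summarized and assessed by paired t-test or Wilcoxon signed-rank test at a significance level of 0.05". Protocol 10.3 describes a descriptive summary plus a transition matrix: "The summary results of 12-lead resting ECG at Baseline and the End of Study Visit will be summarized descriptively".
- **Baseline.** Table 14.3.6.1 takes Screening (V1) as the ECG reference. Under Protocol 7.2.4, subjects who finished the parent study within the last 28 days need no new tracing: "they will be allowed to enter the Extension study without repeating the testosterone measurements, ECG, PE, laboratory and the PSA tests". For laboratory values the baseline is explicit in Protocol 7.2.2: "The End of Study laboratory tests, HgbA1c and PSA assessments for Protocol FP01C-13-001 will be used as the Baseline assessment for this study". Protocol 7.2.3 does the same for urinalysis. Protocol 7.2.4 names no baseline for ECG.

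**The concern.** QT shortens as heart rate rises and lengthens as it falls. A change in raw QT can therefore reflect rate alone, and a true lengthening can be hidden by a faster rate. Safety is the only objective of this extension, ECG change is one of the three named endpoint components, and the protocol itself lists QT/QTc prolongation as a reported event with leuprolide acetate. The one QT test in the plan is applied to the rate-dependent quantity, while the RR needed to correct it sits in the same record.

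At stake are the spread, the extremes and any test of the within-subject corrected change. For a repolarisation risk the individual outliers matter most, and raw QT may point to the wrong subjects. Leaving the formula unstated also leaves its choice open until the data are seen.

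**Working it through.** The plan states no QT figure, effect size or power, so there is nothing of its own to reproduce. The check has a document part and an illustration.

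**Documents.** SAP 10.5, the shells of Tables 14.3.6.1 and 14.3.6.2, Listing 16.2.12 and the protocol were searched for a corrected QT or a correction formula. Only the risk statement in Protocol 5.5 mentions QTc.

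**Single subject.** Fridericia relation: QTcF = QT/(RR/1000)^(1/3) with RR in msec, or QT = QTcF × (60/HR)^(1/3).

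- False signal: with QTcF constant at 420 ms, HR 70 gives QT = 420 × (60/70)^(1/3) = 399.0 ms and HR 65 gives 420 × (60/65)^(1/3) = 408.9 ms. Raw QT rises about 10.0 ms with no corrected change.
- Masked signal: with raw QT constant at 400 ms, HR 70 to 75 moves QTcF from 421.1 to 430.9 ms, a rise of 9.8 ms while the raw row shows 0.
- Over QTcF 400 to 440 ms and starting HR 60 to 80 bpm, a 2 bpm rise shortens raw QT by 2.98 to 4.78 ms and a 10 bpm fall lengthens it by 16.5 to 27.6 ms, with QTcF unchanged.

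**Group test, by formula.** Normal-approximation power is Φ(d/(SD/√n) − 1.96), two-sided 0.05 (sidedness is assumed). Take d = 9.5 ms, the raw-QT shift from HR 70 to 65 at QTcF 400, and an assumed SD of change of 15 to 30 ms. The probability of a significant result is 0.96 to above 0.99 at n = 137 and 0.76 to above 0.99 at n = 70.

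**Simulation.** 4,000 trials per scenario. Assumed, not from the documents:

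- baseline QTcF 420 ms (SD 20) and HR 70 bpm (SD 10);
- SD of within-subject change 10 or 15 ms for QTcF and 5 or 7 bpm for HR;
- n = 70, or n = 137, which is the ceiling in SAP 4.3.

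With no mean shift in HR or QTcF (entries are n = 70 / n = 137):

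| SD of change: QTcF ms, HR bpm | SD of raw QT change, ms | Correlation of raw QT and QTcF change | Same subject has largest rise | Mean largest rise, raw QT, ms | Mean largest rise, QTcF, ms |
|---|---|---|---|---|---|
| 10, 5 | 13.8 / 13.9 | 0.68 / 0.69 | 19.6% / 13.8% | 36.1 / 40.7 | 23.9 / 26.2 |
| 10, 7 | 17.0 / 17.0 | 0.56 / 0.56 | 11.0% / 7.5% | 46.5 / 51.9 | 23.9 / 26.1 |
| 15, 5 | 17.5 / 17.5 | 0.81 / 0.82 | 29.8% / 25.8% | 44.9 / 49.6 | 35.9 / 39.3 |
| 15, 7 | 20.0 / 20.1 | 0.71 / 0.71 | 19.9% / 15.1% | 53.2 / 59.3 | 35.4 / 39.2 |

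Paired t-test rejection at 0.05, range over these settings:

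| Scenario | Raw QT | QTcF |
|---|---|---|
| Mean HR shift +2 or −2 bpm, no QTcF change | 23.3% to 95.8% | 4.4% to 5.5% |
| Mean HR rise 2 bpm, true mean QTcF rise 5 ms | 9.6% to 23.3% | 77.9% to 100% |

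**What is not lost.** Applying Fridericia to the printed mean QT and mean RR recovered the mean QTcF change with an average bias of −0.20 to −0.60 ms. The largest error in a single simulated trial was 1.62 ms in one run and 1.76 ms in a repeat.

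**The case against.** The strongest reply is that the same table exposes the confounder. HR change is printed with a P-value at both visits. In the simulated 2 bpm scenarios without a QTcF change, the HR test itself rejects in 64% to 99.6% of trials, and raw QT is significant without HR in only 0% to 9%. A false QT signal would therefore seldom go unexplained. Mean QTc change can be approximated from the printed means, and individual QTc can be computed from Listing 16.2.12.

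This narrows the concern and is accepted for group means. It does not supply the within-subject spread, extremes or a test. In the masking scenario the HR test rejects in 66% to 99.7% of trials, so a reader would usually see the rate rise but would have no planned corrected test. Values that a reader could work out from a listing are not a prespecified analysis.

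Other points stand as limits:

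- The ECG endpoint is investigator-judged, adverse events are tabulated separately, and the listing has a free-text field for abnormal tracings. The interval rows are supportive.
- Baseline follows 12 months on drug. A QT effect that arose in the parent year is already in it, so neither raw QT nor QTcF change would measure that effect.
- Every numerical input is assumed. The data were generated with an exact cube-root relation, so the near-nominal error rate of QTcF is built in.
- The baseline gap affects every ECG change row, and the testing discrepancy affects all ECG tests. Neither is evidence for the QTc point, but both must be settled before any QTc change can be reported.

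**Conclusion.** The concern holds. The plan reports, and at Day 336 tests, the rate-dependent QT for a risk that the protocol names, and no planned output gives the corrected within-subject change. That omission is certain from the documents. Its consequence is possible rather than shown, because nothing in the documents says that heart rate will shift.

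If the assumed variability is about right, a 2 bpm mean shift is enough to produce or hide a significant raw-QT result. Even without a mean shift, individual rate variation widens the raw-QT changes by roughly a sixth to 70% (17.5/15 = 1.17; 17.0/10 = 1.70) and usually puts the largest rise on a different subject. Group means and the investigator-judged endpoint are not undermined. This is a recommended correction to the analysis, not a flaw that invalidates the study.

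**What to change.** - Prespecify QTcF = QT/(RR/1000)^(1/3) per subject and visit, with RR in msec. Keep raw QT.
- Add QTcF value and change from baseline at Day 168 and Day 336 to Table 14.3.6.1, and a QTcF column to Listing 16.2.12.
- If a change-from-baseline test is kept, apply it to QTcF rather than raw QT. Counts by QTcF category, with cut-offs set in advance by the sponsor, would be useful; a 95% confidence interval is optional.
- Name the ECG baseline. For subjects who enter within 28 days without a repeat tracing, use the parent-study End of Study ECG where QT and RR are available. Report how many subjects have a usable baseline.
- State that baseline is on-drug, so the result describes only further change during the extension.
- Reconcile Synopsis X.4(3), which tests ECG change, with Protocol 10.3, which describes it.

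The cost is one derived variable, a few table rows and one listing column, with no additional ECGs. The one dependency is parent-study ECG data for subjects who enter within 28 days. The documents do not show whether QT and RR are available there, and the same limit already applies to every ECG change row now planned.

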11. COMPUTER METHODS

The data analysis for this study will be generated using SAS® software, Version 9.3 of the SAS System for Windows 7. Copyright© 2013 SAS Institute Inc. SAS and all other SAS Institute Inc. product or service names are registered trademarks or trademarks of SAS Institute Inc., Cary, NC, USA. In addition, graphs will be created by Microsoft Excel 2007 if necessary.

Table of Content

	No.	Item
Demographics and Baseline Characteristics	Table 14.1.1	Summary of Demographics and Baseline Characteristics (Safety Population)
Subject Disposition	Table 14.1.2	Summary of Disposition Status (Safety Population)
	Table 14.1.3	List of Subject Incomplete Study (Safety Population)
	Table 14.1.4	Summary of Study Population (Enrolled Subjects)
Safety	Table 14.3.1.1	Summary of TEAEs (Safety Population)
	Table 14.3.1.2	Summary of Incidence of TEAEs (Safety Population)
	Table 14.3.1.3	Summary of Incidence of TEAEs by Severity (Safety Population)
	Table 14.3.1.4	Summary of Incidence of Drug-Related AEs (Safety Population)
	Table 14.3.1.5	Summary of Incidence of Drug-Related AEs by Severity (Safety Population)
	Table 14.3.1.6	Summary of Incidence of SAEs (Safety Population)
	Table 14.3.1.7	Summary of Incidence of TEAEs >5% (Safety Population)
	Table 14.3.1.8	Summary of Incidence of TEAEs by Severity >5% (Safety Population)
	Table 14.3.1.9	Summary of Incidence of Drug-Related AEs >5% (Safety Population)
	Table 14.3.1.10	Summary of Incidence of Drug-Related AEs by Severity >5% (Safety Population)
	Table 14.3.2	Summary of Study Medication (Safety Population)
	Table 14.3.3.1	Summary of Laboratory Assessments - Hematology (Safety Population)
	Table 14.3.3.2	Summary of Laboratory Assessments - Biochemistry (Safety Population)
	Table 14.3.3.3	Summary of Laboratory Assessments - Urinalysis (Safety Population)
	Table 14.3.3.4	Summary of Laboratory Assessments Transition Status - Hematology (Safety Population)
	Table 14.3.3.5	Summary of Laboratory Assessments Transition Status - Biochemistry (Safety Population)
	Table 14.3.3.6	Summary of Laboratory Assessments Transition Status - Urinalysis (Safety Population)
	Table 14.3.4	Summary of Vital Signs (Safety Population)
	Table 14.3.5.1	Summary of Physical Examination (Safety Population)
	Table 14.3.5.2	Summary of Physical Examination Transition Status (Safety Population)
	Table 14.3.6.1	Summary of ECG (Safety Population)
	Table 14.3.6.2	Summary of ECG Transition Status (Safety Population)

Table 14.1.1: Summary of Demographics and Baseline Characteristics (Safety Population)

Variables / Status	Total (N=XX)
Age (years)*	
n	nn
mean (SD)	xx.x (xx.x)
SE	xx.x
median (min, max)	xx.x (xx.x, xx.x)
Gender	
Male	nn (xx.x%)
Race	
White	nn (xx.x%)
Black	nn (xx.x%)
Asian	nn (xx.x%)
American Indian or Alaska Native	nn (xx.x%)
Native Hawaiian or Pacific Islander	nn (xx.x%)
Other	nn (xx.x%)
Diagnosis (years)**	
n	nn
mean (SD)	xx.x (xx.x)
SE	xx.x
median (min, max)	xx.x (xx.x, xx.x)
TNM	
T_N_M_	nn (xx.x%)
Staging	
III	nn (xx.x%)
IV	nn (xx.x%)
ECOG performance status	
0	nn (xx.x%)
1	nn (xx.x%)
2	nn (xx.x%)

*The age (years) is calculated as (Date of informed consent - Date of birth)/365.25.

**The diagnosis age (years) is calculated as (Date of informed consent - Date of diagnosis)/365.25.

[Program: \\Foresee\\FP01C-13-001\\SAP\\Table\\S_DM.sas]

Table 14.1.2: Summary of Disposition Status (Safety Population)

Variables / Status	Total (N=XX)
Enter by visit	
Screening (V1)	nn (xx.x%)
Day 0 (V2)	nn (xx.x%)
Day 84 (V3)	nn (xx.x%)
Day 168 (V4)	nn (xx.x%)
Day 252 (V5)	nn (xx.x%)
Day 336 (V6/EOS)	nn (xx.x%)
Complete the study	
Yes	nn (xx.x%)
No	nn (xx.x%)
Reason for withdrawal*	
Lost to follow-up	nn (xx.x%)
Subject withdrew consent	nn (xx.x%)
Treating with the prohibited medications will be needed	nn (xx.x%)
Adverse event	nn (xx.x%)
Protocol violation	nn (xx.x%)
Lack of efficacy	nn (xx.x%)
Persistent non-castrate testosterone levels judged by the investigator	nn (xx.x%)
Other	nn (xx.x%)

Percentage of the primary withdrawal reason = 100%[The number of subject(s) in the category / The number of subject(s) who did not complete study]
 [Program: \\Foresee\\FP01C-13-001\\SAP\\Table\\S_DS.sas]

Table 14.1.3: List of Subject Incomplete Study (Safety Population)

Subject No.	Primary Withdraw Reason	Comment
<hr/>		

Table 14.1.4: Summary of Study Population (Enrolled Subjects)

	Variables Status	Total (N=XX)
Safety population		
Included		nn (xx.x%)
Excluded		nn (xx.x%)

Table 14.3.1.1: Summary of TEAEs (Safety Population)

Variables / Status	Previous TEAEs (N=XX)			Newly TEAEs (N=XX)			Total TEAEs (N=XX)		
	E	n	(%)	E	n	(%)	E	n	(%)
TEAEs									
	E	nn	(xx.x%)	E	nn	(xx.x%)	E	nn	(xx.x%)
TEAEs by severity									
Mild	E	nn	(xx.x%)	E	nn	(xx.x%)	E	nn	(xx.x%)
Moderate	E	nn	(xx.x%)	E	nn	(xx.x%)	E	nn	(xx.x%)
Severe	E	nn	(xx.x%)	E	nn	(xx.x%)	E	nn	(xx.x%)
Life-threatening	E	nn	(xx.x%)	E	nn	(xx.x%)	E	nn	(xx.x%)
Death	E	nn	(xx.x%)	E	nn	(xx.x%)	E	nn	(xx.x%)
TEAEs by relationship									
Definite	E	nn	(xx.x%)	E	nn	(xx.x%)	E	nn	(xx.x%)
Possible	E	nn	(xx.x%)	E	nn	(xx.x%)	E	nn	(xx.x%)
Unrelated	E	nn	(xx.x%)	E	nn	(xx.x%)	E	nn	(xx.x%)
Drug-related AEs*									
	E	nn	(xx.x%)	E	nn	(xx.x%)	E	nn	(xx.x%)
Drug-related AEs* by severity									
Mild	E	nn	(xx.x%)	E	nn	(xx.x%)	E	nn	(xx.x%)
Moderate	E	nn	(xx.x%)	E	nn	(xx.x%)	E	nn	(xx.x%)
Severe	E	nn	(xx.x%)	E	nn	(xx.x%)	E	nn	(xx.x%)
Life-threatening	E	nn	(xx.x%)	E	nn	(xx.x%)	E	nn	(xx.x%)
Death	E	nn	(xx.x%)	E	nn	(xx.x%)	E	nn	(xx.x%)
SAEs									
	E	nn	(xx.x%)	E	nn	(xx.x%)	E	nn	(xx.x%)

E is the number of events, n is the number of subjects, and the AE percentage: 100%*The number of subjects with event (n) / Total number of subjects in Safety population (N)

*Relationship to study drug: AE related to study drug will include AEs classified as 'Definite', or 'Possible'. AEs not related to study drug will include AEs that is 'Unrelated'.

[Program: \\Foresee\\FP01C-13-001\\SAP\\Table\\S_AE.sas]

Table 14.3.1.2: Summary of Incidence of TEAEs (Safety Population)

System Organ Class / Preferred Term	Previous TEAEs (N=XX)			Newly TEAEs (N=XX)			Total TEAEs (N=XX)		
	E	n	(%)	E	n	(%)	E	n	(%)
System Organ Class 1									
Preferred Term 1	E	nn	(xx.x%)	E	nn	(xx.x%)	E	nn	(xx.x%)
Preferred Term 2	E	nn	(xx.x%)	E	nn	(xx.x%)	E	nn	(xx.x%)
System Organ Class 2									
Preferred Term 1	E	nn	(xx.x%)	E	nn	(xx.x%)	E	nn	(xx.x%)
Preferred Term 2	E	nn	(xx.x%)	E	nn	(xx.x%)	E	nn	(xx.x%)

E is the number of events, n is the number of subjects, and the AE percentage: 100%*The number of subjects with event (n) / Total number of subjects in Safety population (N)
 [Program: \\Foresee\\FP01C-13-001\\SAP\\Table\\S_AE.sas]

Table 14.3.1.3: Summary of Incidence of TEAEs by Severity (Safety Population)

			Previous TEAEs (N=XX)			Newly TEAEs (N=XX)			Total TEAEs (N=XX)		
	System Organ Class	Preferred Term	E	n	(%)	E	n	(%)	E	n	(%)
Mild AE											
	System Organ Class 1	Preferred Term 1	E	nn	(xx.x%)	E	nn	(xx.x%)	E	nn	(xx.x%)
	System Organ Class 1	Preferred Term 2	E	nn	(xx.x%)	E	nn	(xx.x%)	E	nn	(xx.x%)
	System Organ Class 2	Preferred Term 1	E	nn	(xx.x%)	E	nn	(xx.x%)	E	nn	(xx.x%)
	System Organ Class 2	Preferred Term 2	E	nn	(xx.x%)	E	nn	(xx.x%)	E	nn	(xx.x%)
Moderate AE											
	System Organ Class 1	Preferred Term 1	E	nn	(xx.x%)	E	nn	(xx.x%)	E	nn	(xx.x%)
	System Organ Class 1	Preferred Term 2	E	nn	(xx.x%)	E	nn	(xx.x%)	E	nn	(xx.x%)
	System Organ Class 2	Preferred Term 1	E	nn	(xx.x%)	E	nn	(xx.x%)	E	nn	(xx.x%)
	System Organ Class 2	Preferred Term 2	E	nn	(xx.x%)	E	nn	(xx.x%)	E	nn	(xx.x%)
Severe AE											
	System Organ Class 1	Preferred Term 1	E	nn	(xx.x%)	E	nn	(xx.x%)	E	nn	(xx.x%)
	System Organ Class 1	Preferred Term 2	E	nn	(xx.x%)	E	nn	(xx.x%)	E	nn	(xx.x%)
	System Organ Class 2	Preferred Term 1	E	nn	(xx.x%)	E	nn	(xx.x%)	E	nn	(xx.x%)
	System Organ Class 2	Preferred Term 2	E	nn	(xx.x%)	E	nn	(xx.x%)	E	nn	(xx.x%)
Life-threatening AE											
	System Organ Class 1	Preferred Term 1	E	nn	(xx.x%)	E	nn	(xx.x%)	E	nn	(xx.x%)
	System Organ Class 1	Preferred Term 2	E	nn	(xx.x%)	E	nn	(xx.x%)	E	nn	(xx.x%)
	System Organ Class 2	Preferred Term 1	E	nn	(xx.x%)	E	nn	(xx.x%)	E	nn	(xx.x%)
	System Organ Class 2	Preferred Term 2	E	nn	(xx.x%)	E	nn	(xx.x%)	E	nn	(xx.x%)
Death AE											
	System Organ Class 1	Preferred Term 1	E	nn	(xx.x%)	E	nn	(xx.x%)	E	nn	(xx.x%)
	System Organ Class 1	Preferred Term 2	E	nn	(xx.x%)	E	nn	(xx.x%)	E	nn	(xx.x%)
	System Organ Class 2	Preferred Term 1	E	nn	(xx.x%)	E	nn	(xx.x%)	E	nn	(xx.x%)
	System Organ Class 2	Preferred Term 2	E	nn	(xx.x%)	E	nn	(xx.x%)	E	nn	(xx.x%)

E is the number of events, n is the number of subjects, and the AE percentage: 100%*The number of subjects with event (n) / Total number of subjects in Safety population (N)
[Program: \\Foresee\\FP01C-13-001\\SAP\\Table\\S_AE.sas]

Table 14.3.1.4: Summary of Incidence of Drug-Related AEs (Safety Population)

System Organ Class / Preferred Term	Previous TEAEs (N=XX)			Newly TEAEs (N=XX)			Total TEAEs (N=XX)		
	E	n	(%)	E	n	(%)	E	n	(%)
System Organ Class 1									
Preferred Term 1	E	nn	(xx.x%)	E	nn	(xx.x%)	E	nn	(xx.x%)
Preferred Term 2	E	nn	(xx.x%)	E	nn	(xx.x%)	E	nn	(xx.x%)
System Organ Class 2									
Preferred Term 1	E	nn	(xx.x%)	E	nn	(xx.x%)	E	nn	(xx.x%)
Preferred Term 2	E	nn	(xx.x%)	E	nn	(xx.x%)	E	nn	(xx.x%)

E is the number of events, n is the number of subjects, and the AE percentage: 100%*The number of subjects with event (n) / Total number of subjects in Safety population (N)
 [Program: \\Foresee\\FP01C-13-001\\SAP\\Table\\S_AE.sas]

Table 14.3.1.5: Summary of Incidence of Drug-Related AEs by Severity (Safety Population)

			Previous TEAEs (N=XX)			Newly TEAEs (N=XX)			Total TEAEs (N=XX)		
	System Organ Class	Preferred Term	E	n	(%)	E	n	(%)	E	n	(%)
Mild AE											
System Organ Class 1	Preferred Term 1	E	nn	(xx.x%)	E	nn	(xx.x%)	E	nn	(xx.x%)	
System Organ Class 1	Preferred Term 2	E	nn	(xx.x%)	E	nn	(xx.x%)	E	nn	(xx.x%)	
System Organ Class 2	Preferred Term 1	E	nn	(xx.x%)	E	nn	(xx.x%)	E	nn	(xx.x%)	
System Organ Class 2	Preferred Term 2	E	nn	(xx.x%)	E	nn	(xx.x%)	E	nn	(xx.x%)	
Moderate AE											
System Organ Class 1	Preferred Term 1	E	nn	(xx.x%)	E	nn	(xx.x%)	E	nn	(xx.x%)	
System Organ Class 1	Preferred Term 2	E	nn	(xx.x%)	E	nn	(xx.x%)	E	nn	(xx.x%)	
System Organ Class 2	Preferred Term 1	E	nn	(xx.x%)	E	nn	(xx.x%)	E	nn	(xx.x%)	
System Organ Class 2	Preferred Term 2	E	nn	(xx.x%)	E	nn	(xx.x%)	E	nn	(xx.x%)	
Severe AE											
System Organ Class 1	Preferred Term 1	E	nn	(xx.x%)	E	nn	(xx.x%)	E	nn	(xx.x%)	
System Organ Class 1	Preferred Term 2	E	nn	(xx.x%)	E	nn	(xx.x%)	E	nn	(xx.x%)	
System Organ Class 2	Preferred Term 1	E	nn	(xx.x%)	E	nn	(xx.x%)	E	nn	(xx.x%)	
System Organ Class 2	Preferred Term 2	E	nn	(xx.x%)	E	nn	(xx.x%)	E	nn	(xx.x%)	
Life-threatening AE											
System Organ Class 1	Preferred Term 1	E	nn	(xx.x%)	E	nn	(xx.x%)	E	nn	(xx.x%)	
System Organ Class 1	Preferred Term 2	E	nn	(xx.x%)	E	nn	(xx.x%)	E	nn	(xx.x%)	
System Organ Class 2	Preferred Term 1	E	nn	(xx.x%)	E	nn	(xx.x%)	E	nn	(xx.x%)	
System Organ Class 2	Preferred Term 2	E	nn	(xx.x%)	E	nn	(xx.x%)	E	nn	(xx.x%)	
Death AE											
System Organ Class 1	Preferred Term 1	E	nn	(xx.x%)	E	nn	(xx.x%)	E	nn	(xx.x%)	
System Organ Class 1	Preferred Term 2	E	nn	(xx.x%)	E	nn	(xx.x%)	E	nn	(xx.x%)	
System Organ Class 2	Preferred Term 1	E	nn	(xx.x%)	E	nn	(xx.x%)	E	nn	(xx.x%)	
System Organ Class 2	Preferred Term 2	E	nn	(xx.x%)	E	nn	(xx.x%)	E	nn	(xx.x%)	

E is the number of events, n is the number of subjects, and the AE percentage: 100%*The number of subjects with event (n) / Total number of subjects in Safety population (N)
[Program: \\Foresee\\FP01C-13-001\\SAP\\Table\\S_AE.sas]

Table 14.3.1.6: Summary of Incidence of SAEs (Safety Population)

System Organ Class / Preferred Term	Previous TEAEs (N=XX)			Newly TEAEs (N=XX)			Total TEAEs (N=XX)		
	E	n	(%)	E	n	(%)	E	n	(%)
System Organ Class 1									
Preferred Term 1	E	nn	(xx.x%)	E	nn	(xx.x%)	E	nn	(xx.x%)
Preferred Term 2	E	nn	(xx.x%)	E	nn	(xx.x%)	E	nn	(xx.x%)
System Organ Class 2									
Preferred Term 1	E	nn	(xx.x%)	E	nn	(xx.x%)	E	nn	(xx.x%)
Preferred Term 2	E	nn	(xx.x%)	E	nn	(xx.x%)	E	nn	(xx.x%)

E is the number of events, n is the number of subjects, and the AE percentage: 100%*The number of subjects with event (n) / Total number of subjects in Safety population (N)
 [Program: \\Foresee\\FP01C-13-001\\SAP\\Table\\S_AE.sas]

Table 14.3.1.7: Summary of Incidence of TEAEs >5% (Safety Population)

System Organ Class / Preferred Term	Previous TEAEs (N=XX)			Newly TEAEs (N=XX)			Total TEAEs (N=XX)		
	E	n	(%)	E	n	(%)	E	n	(%)
System Organ Class 1									
Preferred Term 1	E	nn	(xx.x%)	E	nn	(xx.x%)	E	nn	(xx.x%)
Preferred Term 2	E	nn	(xx.x%)	E	nn	(xx.x%)	E	nn	(xx.x%)
System Organ Class 2									
Preferred Term 1	E	nn	(xx.x%)	E	nn	(xx.x%)	E	nn	(xx.x%)
Preferred Term 2	E	nn	(xx.x%)	E	nn	(xx.x%)	E	nn	(xx.x%)

E is the number of events, n is the number of subjects, and the AE percentage: 100%*The number of subjects with event (n) / Total number of subjects in Safety population (N)
 [Program: \\Foresee\\FP01C-13-001\\SAP\\Table\\S_AE.sas]

Table 14.3.1.8: Summary of Incidence of TEAEs by Severity >5% (Safety Population)

			Previous TEAEs (N=XX)			Newly TEAEs (N=XX)			Total TEAEs (N=XX)		
	System Organ Class	Preferred Term	E	n	(%)	E	n	(%)	E	n	(%)
Mild AE											
	System Organ Class 1	Preferred Term 1	E	nn	(xx.x%)	E	nn	(xx.x%)	E	nn	(xx.x%)
	System Organ Class 1	Preferred Term 2	E	nn	(xx.x%)	E	nn	(xx.x%)	E	nn	(xx.x%)
	System Organ Class 2	Preferred Term 1	E	nn	(xx.x%)	E	nn	(xx.x%)	E	nn	(xx.x%)
	System Organ Class 2	Preferred Term 2	E	nn	(xx.x%)	E	nn	(xx.x%)	E	nn	(xx.x%)
Moderate AE											
	System Organ Class 1	Preferred Term 1	E	nn	(xx.x%)	E	nn	(xx.x%)	E	nn	(xx.x%)
	System Organ Class 1	Preferred Term 2	E	nn	(xx.x%)	E	nn	(xx.x%)	E	nn	(xx.x%)
	System Organ Class 2	Preferred Term 1	E	nn	(xx.x%)	E	nn	(xx.x%)	E	nn	(xx.x%)
	System Organ Class 2	Preferred Term 2	E	nn	(xx.x%)	E	nn	(xx.x%)	E	nn	(xx.x%)
Severe AE											
	System Organ Class 1	Preferred Term 1	E	nn	(xx.x%)	E	nn	(xx.x%)	E	nn	(xx.x%)
	System Organ Class 1	Preferred Term 2	E	nn	(xx.x%)	E	nn	(xx.x%)	E	nn	(xx.x%)
	System Organ Class 2	Preferred Term 1	E	nn	(xx.x%)	E	nn	(xx.x%)	E	nn	(xx.x%)
	System Organ Class 2	Preferred Term 2	E	nn	(xx.x%)	E	nn	(xx.x%)	E	nn	(xx.x%)
Life-threatening AE											
	System Organ Class 1	Preferred Term 1	E	nn	(xx.x%)	E	nn	(xx.x%)	E	nn	(xx.x%)
	System Organ Class 1	Preferred Term 2	E	nn	(xx.x%)	E	nn	(xx.x%)	E	nn	(xx.x%)
	System Organ Class 2	Preferred Term 1	E	nn	(xx.x%)	E	nn	(xx.x%)	E	nn	(xx.x%)
	System Organ Class 2	Preferred Term 2	E	nn	(xx.x%)	E	nn	(xx.x%)	E	nn	(xx.x%)
Death AE											
	System Organ Class 1	Preferred Term 1	E	nn	(xx.x%)	E	nn	(xx.x%)	E	nn	(xx.x%)
	System Organ Class 1	Preferred Term 2	E	nn	(xx.x%)	E	nn	(xx.x%)	E	nn	(xx.x%)
	System Organ Class 2	Preferred Term 1	E	nn	(xx.x%)	E	nn	(xx.x%)	E	nn	(xx.x%)
	System Organ Class 2	Preferred Term 2	E	nn	(xx.x%)	E	nn	(xx.x%)	E	nn	(xx.x%)

E is the number of events, n is the number of subjects, and the AE percentage: 100%*The number of subjects with event (n) / Total number of subjects in Safety population (N)
[Program: \\Foresee\\FP01C-13-001\\SAP\\Table\\S_AE.sas]

Table 14.3.1.9: Summary of Incidence of Drug-Related AEs >5% (Safety Population)

System Organ Class / Preferred Term	Previous TEAEs (N=XX)			Newly TEAEs (N=XX)			Total TEAEs (N=XX)		
	E	n	(%)	E	n	(%)	E	n	(%)
System Organ Class 1									
Preferred Term 1	E	nn	(xx.x%)	E	nn	(xx.x%)	E	nn	(xx.x%)
Preferred Term 2	E	nn	(xx.x%)	E	nn	(xx.x%)	E	nn	(xx.x%)
System Organ Class 2									
Preferred Term 1	E	nn	(xx.x%)	E	nn	(xx.x%)	E	nn	(xx.x%)
Preferred Term 2	E	nn	(xx.x%)	E	nn	(xx.x%)	E	nn	(xx.x%)

E is the number of events, n is the number of subjects, and the AE percentage: 100%*The number of subjects with event (n) / Total number of subjects in Safety population (N)
 [Program: \\Foresee\\FP01C-13-001\\SAP\\Table\\S_AE.sas]

Table 14.3.1.10: Summary of Incidence of Drug-Related AEs by Severity >5% (Safety Population)

			Previous TEAEs (N=XX)			Newly TEAEs (N=XX)			Total TEAEs (N=XX)		
	System Organ Class	Preferred Term	E	n	(%)	E	n	(%)	E	n	(%)
Mild AE											
System Organ Class 1	Preferred Term 1	E	nn	(xx.x%)	E	nn	(xx.x%)	E	nn	(xx.x%)	
System Organ Class 1	Preferred Term 2	E	nn	(xx.x%)	E	nn	(xx.x%)	E	nn	(xx.x%)	
System Organ Class 2	Preferred Term 1	E	nn	(xx.x%)	E	nn	(xx.x%)	E	nn	(xx.x%)	
System Organ Class 2	Preferred Term 2	E	nn	(xx.x%)	E	nn	(xx.x%)	E	nn	(xx.x%)	
Moderate AE											
System Organ Class 1	Preferred Term 1	E	nn	(xx.x%)	E	nn	(xx.x%)	E	nn	(xx.x%)	
System Organ Class 1	Preferred Term 2	E	nn	(xx.x%)	E	nn	(xx.x%)	E	nn	(xx.x%)	
System Organ Class 2	Preferred Term 1	E	nn	(xx.x%)	E	nn	(xx.x%)	E	nn	(xx.x%)	
System Organ Class 2	Preferred Term 2	E	nn	(xx.x%)	E	nn	(xx.x%)	E	nn	(xx.x%)	
Severe AE											
System Organ Class 1	Preferred Term 1	E	nn	(xx.x%)	E	nn	(xx.x%)	E	nn	(xx.x%)	
System Organ Class 1	Preferred Term 2	E	nn	(xx.x%)	E	nn	(xx.x%)	E	nn	(xx.x%)	
System Organ Class 2	Preferred Term 1	E	nn	(xx.x%)	E	nn	(xx.x%)	E	nn	(xx.x%)	
System Organ Class 2	Preferred Term 2	E	nn	(xx.x%)	E	nn	(xx.x%)	E	nn	(xx.x%)	
Life-threatening AE											
System Organ Class 1	Preferred Term 1	E	nn	(xx.x%)	E	nn	(xx.x%)	E	nn	(xx.x%)	
System Organ Class 1	Preferred Term 2	E	nn	(xx.x%)	E	nn	(xx.x%)	E	nn	(xx.x%)	
System Organ Class 2	Preferred Term 1	E	nn	(xx.x%)	E	nn	(xx.x%)	E	nn	(xx.x%)	
System Organ Class 2	Preferred Term 2	E	nn	(xx.x%)	E	nn	(xx.x%)	E	nn	(xx.x%)	
Death AE											
System Organ Class 1	Preferred Term 1	E	nn	(xx.x%)	E	nn	(xx.x%)	E	nn	(xx.x%)	
System Organ Class 1	Preferred Term 2	E	nn	(xx.x%)	E	nn	(xx.x%)	E	nn	(xx.x%)	
System Organ Class 2	Preferred Term 1	E	nn	(xx.x%)	E	nn	(xx.x%)	E	nn	(xx.x%)	
System Organ Class 2	Preferred Term 2	E	nn	(xx.x%)	E	nn	(xx.x%)	E	nn	(xx.x%)	

E is the number of events, n is the number of subjects, and the AE percentage: 100%*The number of subjects with event (n) / Total number of subjects in Safety population (N)
[Program: \\Foresee\\FP01C-13-001\\SAP\\Table\\S_AE.sas]

Table 14.3.2: Summary of Study Medication (Safety Population)

Variables / Status	Total (N=XX)
Received first administration	
Yes	nn (xx.x%)
No	nn (xx.x%)
Received second administration	
Yes	nn (xx.x%)
No	nn (xx.x%)
Treatment duration (days)	
n	nn
mean (SD)	xx.x (xx.x)
SE	xx.x
median (min, max)	xx.x (xx.x, xx.x)
Study duration (days)	
n	nn
mean (SD)	xx.x (xx.x)
SE	xx.x
median (min, max)	xx.x (xx.x, xx.x)

Treatment duration (days) is defined as (last administered date – first administered date + 1); and study duration (days) is defined as (last visit date – first administered date + 1).
 [Program: \\Foresee\\FP01C-13-001\\SAP\\Table\\S_EX.sas]

Table 14.3.3.1: Summary of Laboratory Assessments - Hematology (Safety Population)

Variables / Status	Total (N=XX)
Hematology at Screening (V1)	
n	nn
mean (SD)	xx.x (xx.x)
SE	nn (xx.x%)
median (min, max)	xx.x (xx.x, xx.x)
Normal	nn (xx.x%)
Abnormal - NCS	nn (xx.x%)
Abnormal - CS	nn (xx.x%)
Not Done	nn (xx.x%)
Hematology on Day 168 (V4)	
n	nn
mean (SD)	xx.x (xx.x)
SE	nn (xx.x%)
median (min, max)	xx.x (xx.x, xx.x)
Normal	nn (xx.x%)
Abnormal - NCS	nn (xx.x%)
Abnormal - CS	nn (xx.x%)
Not Done	nn (xx.x%)
Hematology on Day 336 (V6/EOS)	
n	nn
mean (SD)	xx.x (xx.x)
SE	nn (xx.x%)
median (min, max)	xx.x (xx.x, xx.x)
Normal	nn (xx.x%)
Abnormal - NCS	nn (xx.x%)
Abnormal - CS	nn (xx.x%)
Not Done	nn (xx.x%)
Hematology change on Day 168 (V4)	
n	nn

*Paired T test or Wilcoxon signed rank test will be used to test the change from baseline for continuous variables.
 [Program: \\Foresee\\FP01C-13-001\\SAP\\Table\\S_LB.sas]

Table 14.3.3.1: Summary of Laboratory Assessments - Hematology (Safety Population)

Variables / Status	Total (N=XX)
